### **9.5.8.2.27 Week 48**

- Obtain 2 blood samples for measurement of sUA within 48 hours prior to the pegloticase infusion at this visit. One sample will be tested for sUA at the site's Local Laboratory

and one sample will be shipped to the Central Laboratory for testing. If a subject's previous visit pre-infusion sUA (local or central laboratory) is less than 6 mg/dl; it will be allowable to draw the local pre-infusion sUA sample on the same day and similar time as the sample to send to the central laboratory; however if the prior visit pre-infusion sUA sample was greater than 6 mg/dl (local or central laboratory), a local sUA sample will need to be collected and read out prior to the pegloticase infusion to be certain the subject has not met the stopping rule. To note: It is allowable for the Local and Central Laboratory sUA samples to be drawn on different days or times so long as both samples are drawn within 48 hours prior to the infusion. (see [Section 9.5.1.1](#)).

- Stopping rule: Subjects with an sUA level  $>6$  mg/dL at 2 consecutive study visits beginning with the Week 2 Visit (not including post-infusion samples) will subsequently discontinue treatment and remain in the study.
- Administer MTX/placebo for MTX  $\geq 60$  minutes prior to pegloticase infusion if subject has not taken MTX/placebo for MTX within the previous 1 to 3 days.
- Document gout flares and intensity.
- Record vital signs (blood pressure, respiratory rate, temperature, and heart rate) prior to the pegloticase infusion and any time after the end of the infusion, but prior to discharge. (See [Section 9.5.4.4](#)). During the pre-infusion blood pressure collection, at sites who participate and from subjects who consent, optional intensive BP collections will be obtained. For this optional collection, three blood pressure measurements should be performed, at least 2 minutes apart, with BP readings measured to the nearest mm Hg prior to pegloticase infusion. If any of the 3 systolic blood pressure measurements differed by more than 8 mm Hg or if diastolic measurements differed by more than 5 mm Hg, repeat sets of 3 sitting blood pressure measurements will be obtained until the difference is less than 8 mm Hg for systolic and less than 5 mm Hg for diastolic.
- Assess MTX/placebo for MTX compliance and re-dispense MTX/placebo for MTX.
- Ask Yes/No question regarding folic acid, gout flare prophylaxis, and IR prophylaxis compliance.
- Fill gout prophylaxis, fexofenadine, acetaminophen, and folic acid prescriptions, as needed.
- Obtain a urine sample from all females of childbearing potential for performance of a pregnancy test.
- Administer IR prophylaxis (i.e., fexofenadine, acetaminophen, and methylprednisolone) (see [Section 9.4.1.3](#)).

- Administer pegloticase and record date, volume, and duration of infusion, and start/stop (inclusive of 10-mL flush) times of dosing.
- Obtain a blood sample (1 sample) for measurement of sUA any time after the end of the infusion, prior to discharge from the site.
- Inquire about AEs and concomitant medication use.

#### 9.5.8.2.28 Week 50

- Obtain 2 blood samples for measurement of sUA within 48 hours prior to the pegloticase infusion at this visit. One sample will be tested for sUA at the site's Local Laboratory and one sample will be shipped to the Central Laboratory for testing. If a subject's previous visit pre-infusion sUA (local or central laboratory) is less than 6 mg/dl; it will be allowable to draw the local pre-infusion sUA sample on the same day and similar time as the sample to send to the central laboratory; however if the prior visit pre-infusion sUA sample was greater than 6 mg/dl (local or central laboratory), a local sUA sample will need to be collected and read out prior to the pegloticase infusion to be certain the subject has not met the stopping rule. To note: It is allowable for the Local and Central Laboratory sUA samples to be drawn on different days or times so long as both samples are drawn within 48 hours prior to the infusion (see [Section 9.5.1.1](#)).
- Stopping rule: Subjects with an sUA level  $>6$  mg/dL at 2 consecutive study visits beginning with the Week 2 Visit (not including post-infusion samples) will subsequently discontinue treatment and remain in the study.
- Administer MTX/placebo for MTX  $\geq 60$  minutes prior to pegloticase infusion if subject has not taken MTX/placebo for MTX within the previous 1 to 3 days.
- Document gout flares and intensity.
- Record vital signs (blood pressure, respiratory rate, temperature, and heart rate) prior to the pegloticase infusion and any time after the end of the infusion, but prior to discharge. (See [Section 9.5.4.4](#)).
- Assess MTX/placebo for MTX compliance and re-dispense MTX/placebo for MTX.
- Ask Yes/No question regarding folic acid, gout flare prophylaxis, and IR prophylaxis compliance.
- Fill gout prophylaxis, fexofenadine, acetaminophen, and folic acid prescriptions, as needed.
- Obtain a urine sample from all females of childbearing potential for performance of a pregnancy test.

- Administer IR prophylaxis (i.e., fexofenadine, acetaminophen, and methylprednisolone) (see [Section 9.4.1.3](#)).
- Administer pegloticase and record date, volume, and duration of infusion, and start/stop (inclusive of 10-mL flush) times of dosing.
- Obtain a blood sample (1 sample) for measurement of sUA any time after the end of the infusion, prior to discharge from the site.
- Inquire about AEs and concomitant medication use.

**Note:** MTX will be taken one week following the Week 50 Visit and Folic Acid will be taken until just prior to the Week 52 Visit.

### 9.5.8.3 End of Pegloticase Infusions Visit

Subjects who end pegloticase infusions prior to Week 52 will complete the End of Pegloticase Infusions Visit procedures following their final infusion. Subjects should continue to participate in all visits through the end of the study. Subjects must complete selected study visits at the study site during key efficacy and safety collections at Weeks 12, 14, 20, 21, 22, 23, 24, 32, 34, 36, 48, 50 and 52/End of Study/Early Termination, so that sUA labs and other key assessments can be completed. During visits between these key efficacy and safety collection visits, in subjects who have stopped infusions, subjects may complete study visits in person or via a telephone visit option to collect AEs, conmeds and gout flare information (See [9.3.3.1.1](#)).

The following procedures will be completed at the End of Pegloticase Visit:

- Investigator review of clinical status and subject treatment goals.
- Document gout flares and intensity.
- Perform a targeted physical examination (at a minimum this should include heart, lungs and abdominal examination).
- Record vital signs (blood pressure, respiratory rate, temperature, and heart rate) prior to discharge. (See [Section 9.5.4.4](#)). At sites that participate and from subjects who consent, during the BP collection, optional intensive BP collections will be obtained. For this optional collection, three blood pressure measurements should be performed, at least 2 minutes apart, with BP readings measured to the nearest mm Hg prior to pegloticase infusion. If any of the 3 systolic blood pressure measurements differed by more than 8 mm Hg or if diastolic measurements differed by more than 5 mm Hg, repeat sets of 3 sitting blood pressure measurements will be obtained until the difference is less than 8 mm Hg for systolic and less than 5 mm Hg for diastolic.
- Record weight.

- Collect swollen/tender joint counts; administer HAQ; and record physician global assessments.
- Assess MTX/placebo for MTX compliance.
- Ask Yes/No question regarding folic acid, gout flare prophylaxis compliance.
- Digital photography of hands and feet.
- For sites with DECT capability, and subjects who provide consent, an optional DECT will be obtained. DECT may be completed within +/- 10 days of the scheduled visit. Subjects who end pegloticase infusions prior to Week 52 should follow the scheduled timepoints but avoid a repeat DECT scan within 6 weeks of a prior scan.
- For sites with X-ray capability, and subjects who provide consent, an optional X-ray of the hands and feet will be obtained. The X-ray may be completed within +/- 10 days of the scheduled visit. Subjects who end pegloticase infusions prior to Week 52 should follow the scheduled timepoints but avoid a repeat X-ray within 3 months of a prior X-ray.
- Obtain a urine sample from all females of childbearing potential for performance of a pregnancy test.
- Obtain blood samples for hematology and clinical chemistry analysis.
- Obtain a urine sample for albumin:creatinine ratio.
- Obtain blood and urine samples for allantoin collection.
- Obtain blood samples for pegloticase PK analysis.
- Obtain blood samples for anti-PEG and anti-uricase IgG antibodies.
- Obtain optional whole blood and serum samples from subjects who consent for future analysis.
- Obtain a blood sample (1 sample) for measurement of sUA.
- Inquire about AEs and concomitant medication use.

#### **9.5.8.4 Week 52/End of Study/Early Termination Visit**

- Investigator review of clinical status and subject treatment goals.
- Document gout flares and intensity.

- Perform a targeted physical examination (at a minimum this should include heart, lungs and abdominal examination).
- Record vital signs (blood pressure, respiratory rate, temperature, and heart rate) prior to discharge. (See [Section 9.5.4.4](#)). At sites that participate and from subjects who consent, during the BP collection, optional intensive BP collections will be obtained. For this optional collection, three blood pressure measurements should be performed, at least 2 minutes apart, with BP readings measured to the nearest mm Hg prior to pegloticase infusion. If any of the 3 systolic blood pressure measurements differed by more than 8 mm Hg or if diastolic measurements differed by more than 5 mm Hg, repeat sets of 3 sitting blood pressure measurements will be obtained until the difference is less than 8 mm Hg for systolic and less than 5 mm Hg for diastolic.
- Record weight.
- Collect swollen/tender joint counts; administer HAQ; and record physician global assessments.
- Digital photography of hands and feet.
- For sites with DECT capability, and subjects who provide consent, an optional DECT will be obtained. DECT may be completed within +/- 10 days of the scheduled visit.
- For sites with X-ray capability, and subjects who provide consent, an optional X-ray of the hands and feet will be obtained. The X-ray may be completed within +/- 10 days of the scheduled visit.
- Assess MTX/placebo for MTX compliance.
- Ask Yes/No question regarding folic acid compliance.
- Obtain a urine sample from all females of childbearing potential for performance of a pregnancy test.
- Obtain blood samples for hematology and clinical chemistry analysis.
- Obtain a urine sample for albumin:creatinine ratio.
- Obtain blood and urine samples for allantoin collection.
- Obtain blood samples for pegloticase PK analysis.
- Obtain blood samples for anti-PEG and anti-uricase IgG antibodies.
- Obtain optional whole blood and serum samples from subjects who consent for future analysis.

- Obtain a blood sample (1 sample) for measurement of sUA.
- Inquire about AEs and concomitant medication use.

#### **9.5.8.6 MTX Partner Pregnancy Follow-up**

Subjects who are non-vasectomized males will be asked 3 months after MTX or placebo for MTX discontinuation regarding partner pregnancy. This will occur at a scheduled visit or by a phone/email visit.

#### **9.5.8.7 Post Treatment Follow-up**

The intent is to obtain at least 6 months of follow-up on each subject after cessation of pegloticase infusions. If these 6 months occur prior to end of study at Week 52, such as in the case of a subject who ends pegloticase infusions on or before Week 24, there will be no follow-up visits after the Week 52/End of Study Visit. For subjects who end pegloticase infusions between Weeks 26 and 36, there will be at least 3 months of follow-up while the subject remains on-study prior to Week 52, and then one follow-up visit after the Week 52/End of Study Visit. For subjects who end pegloticase infusions between Weeks 38 and 52, there will be two follow-up visits at intervals of 3 months apart after the Week 52/End of Study Visit. The following procedures will be completed at the 3 and 6 month Post Treatment Follow-up Visits:

- Document gout flares and intensity.
- Record vital signs (blood pressure, respiratory rate, temperature, and heart rate) prior to discharge. (See [Section 9.5.4.4](#)).
- Perform a targeted physical examination (at a minimum this should include heart, lungs and abdominal examination).
- Record weight.
- Collect swollen/tender joint counts; administer HAQ; and record physician global assessments.
- Digital photography of hands and feet.
- Obtain blood samples for hematology and clinical chemistry analysis.
- Obtain a blood sample (1 sample) for measurement of sUA.

- Obtain blood samples for anti-PEG and anti-uricase IgG antibodies (3 Month Post Treatment Follow-up Visit only).
- Inquire about AEs and concomitant medication use.
- For subjects that completed 52 weeks of treatment and consent to the additional optional DECT assessment, collect a DECT scan at the 6 month Follow-up visit.

## 9.6 Statistical Methods and Determination of Sample Size

### 9.6.1 Endpoints

#### 9.6.1.1 Primary Endpoint

The primary efficacy endpoint is the proportion of Month 6 (Weeks 20, 21, 22, 23 and 24) responders, defined as subjects achieving and maintaining sUA <6 mg/dL for at least 80% of the time during Month 6.

#### 9.6.1.2 Secondary Endpoints

The secondary efficacy endpoints (analyzed sequentially) are:

1. The proportion of Month 12 (Weeks 48, 50, and 52) responders, defined as subjects achieving and maintaining sUA <6 mg/dL for at least 80% of the time during Month 12.
2. The proportion of subjects with complete resolution of  $\geq 1$  tophi (using digital photography) at Week 52 in subjects with tophi at baseline.
3. The mean change from baseline in HAQ-DI score at Week 52.
4. The mean change from baseline in HAQ Pain score at Week 52.
5. The mean change from baseline in HAQ Health score at Week 52.

### 9.6.1.3 Exploratory Endpoints

The exploratory efficacy endpoints are:

- The mean change from baseline to Weeks 14, 24, and 52 in urate deposition volume and bone erosions due to gout based on DECT.
- The mean change from baseline to Weeks 24 and 52 in bone erosions due to gout based on X-rays of the hands and feet.
- The proportion of subjects with complete resolution of  $\geq 1$  tophi (using digital photography) at Weeks 24 and 36 in subjects with tophi at baseline.
- The mean change from baseline in tophus size (long axis measured using digital photography) to Weeks 14, 24, 36 and 52 in subjects with tophus present at baseline.
- The proportion of Month 9 (Weeks 32, 34, and 36) responders, defined as subjects achieving and maintaining sUA  $<6$  mg/dL for at least 80% of the time during Month 9.
- The proportion of Month 3 (Weeks 10, 12, and 14) responders, defined as subjects achieving and maintaining sUA  $<6$  mg/dL for at least 80% of the time during Month 3.
- The proportion of overall responders, defined as subjects achieving and maintaining sUA  $<6$  mg/dL for at least 80% of the time during Month 3 (Weeks 10, 12, and 14) and Month 6 (Weeks 20, 21, 22, 23 and 24) combined.
- The proportion of 5 mg/dL responders during each time interval (Month 3, Month 6, Month 9 and Month 12), defined as subjects achieving and maintaining sUA  $<5$  mg/dL for at least 80% of the time during each time interval.
- The mean change from baseline in sUA at Weeks 14, 24, 36 and 52.
- The time to first sUA  $> 6$  mg/dL.
- The time to two consecutive sUA  $> 6$  mg/dL (stopping rule).
- The percentage of non-hyperuricemic (sUA  $< 6$  mg/dL) time during Months 3, 6, 9 and 12.
- The mean change from baseline in HAQ Pain score at Weeks 14, 24, and 36.
- The mean change from baseline in HAQ Health score at Weeks 14, 24, and 36.
- The mean change from baseline in HAQ-DI score at Weeks 14, 24, and 36.
- The mean change from baseline in tender joint count (68-point scale) at Weeks 14, 24, 36 and 52.
- The mean change from baseline in swollen joint count (66-point scale) at Weeks 14, 24, 36 and 52.
- The mean change from baseline in number of tender or swollen joints at Weeks 14, 24, 36 and 52.
- The mean change from baseline in physician global assessment of gout at Weeks 14, 24, 36 and 52.
- The proportion of subjects achieving 20%, 50%, or 70% improvement based on gout chronic response criteria at Weeks 14, 24, 36 and 52.

- The mean change from baseline in SBP and DBP to each visit.

#### **9.6.1.4 Pharmacokinetic and Anti-drug Antibody Endpoints**

The PK and anti-drug antibody endpoints are:

- PK of pegloticase.
- MTX polyglutamate concentrations.
- The incidence of anti-PEG and anti-Uricase IgG antibodies.

#### **9.6.1.5 Safety and Tolerability Endpoints**

Safety and tolerability objectives are:

- AE/SAE profile overall and potentially attributed to the combination of pegloticase and MTX
  - Incidence of AESI: IRs, anaphylaxis, gout flares, cardiovascular events
- Laboratory tests
- Vital signs and physical examination

### **9.6.2 Populations for Analysis**

The following analysis populations will be defined for this study:

- Intent-to-treat population (ITT): all randomized subjects
- Modified intention-to-treat (mITT) population: all randomized subjects who receive at least 1 dose of pegloticase
- Per-protocol population (PP): all randomized subjects who receive at least 1 dose of pegloticase, are taking the 15 mg dose of MTX or placebo for MTX at the time of first pegloticase dose, and have no major protocol deviations that would challenge the validity of the data
- Pharmacokinetic (PK) population: all randomized subjects who receive at least one dose of pegloticase and have a post-pegloticase sample evaluable for PK analysis
- Safety population: all randomized subjects who take at least one dose of blinded MTX or placebo for MTX
- MTX population: all subjects who take at least one dose of MTX

The ITT and mITT populations will be used for analysis of efficacy data; subjects will be analyzed according to the treatment to which they were randomized. The PP population will be used for analysis of select efficacy endpoints; subjects will be analyzed according to the treatment received. The safety population will be used for analysis of safety data; subjects will be analyzed according to the treatment received. The MTX population will be used for analysis of safety data during the Run-In period prior to randomization.

### **9.6.3 Demographic Variables**

Demographic data, including age, race, and gender, medical history, and other disease characteristics, will be summarized using descriptive statistics. Listings will include all screened subjects.

### **9.6.4 Subject Disposition**

The number of subjects in each population and the number and percentage of subjects who completed the study and who discontinued the study prematurely, and who completed pegloticase treatment and who discontinued treatment prematurely, along with the reasons for discontinuation will be summarized for each study period.

### **9.6.5 Efficacy Endpoint Analysis**

Efficacy analyses will be performed using the ITT and mITT populations, with select endpoints analyzed using the PP population. Continuous variables will be summarized using descriptive statistics (number of subjects, mean, median, standard deviation, minimum, and maximum). Categorical variables will be summarized using frequencies and percentages. Unless otherwise specified, baseline is defined as the last non-missing observation prior to the first dose of MTX.

#### **9.6.5.1 Primary and Secondary Endpoint Analysis**

The primary analysis will be conducted in the ITT population. The primary efficacy endpoint is the proportion of responders during Month 6. A responder is defined as a subject for whom the proportion of time that the sUA-time curve is <6 mg/dL during the analysis interval is at least 80%. The proportion of time that the sUA level is below 6 mg/dL is defined as the ratio of the time during which the sUA level remains below 6 mg/dL (using linear interpolation, if necessary) to the entire time interval during Month 6. A subject will be declared a non-responder if the subject had 2 sUA levels >6 mg/dL at 2 consecutive study visits beginning with the Week 2 Visit prior to or during Month 6. Additionally, a subject who withdraws from study treatment for any reason other than the stopping rule after randomization and prior to or during Month 6 (for the primary endpoint) or Months 12 (for the secondary endpoint) will be considered a non-responder at the time of withdrawal (and for all subsequent time points) if sUA values are not collected at the planned time points. Sensitivity analyses of the primary and secondary endpoints will include data (if available) for subjects who discontinue treatment due to stopping rule and remain on study. Special consideration may be given to subjects who discontinue the study or miss visits due to reasons related to the COVID-19 pandemic.

The analysis of the primary endpoint and the secondary responder endpoints will assess risk difference (difference in response proportions) in a stratified analysis. The analysis will use Cochran-Mantel-Haenszel (CMH) weighting to estimate the common risk difference within strata and to estimate the standard error of the common risk difference. Stratification for the analysis will use the same factor as was used to stratify randomization, presence of tophi (yes, no). The difference in response rates, comparing pegloticase with MTX vs. pegloticase with placebo for MTX, will be estimated along with the corresponding 95% confidence interval (CI) and p-value.

Subjects with resolution of  $\geq 1$  tophi are subjects with an overall tophus response of complete response (i.e. complete response in at least one tophi and no evidence of progressive disease, see Section 9.5.1.6.1). The difference in the proportion of subjects with resolution of  $\geq 1$  tophi at Week 52 between pegloticase with MTX and pegloticase with placebo for MTX will be tested with a chi-square test, and the difference in rates will be estimated along with the corresponding 95% confidence interval (CI) and p-value.

The change from baseline to Week 52 for HAQ-DI, HAQ pain score, and HAQ health score to each visit and overall will be analyzed with a mixed model repeated measures (MMRM) analysis of covariance (ANCOVA) model with a term for baseline score, tophi presence at baseline (except for analyses of tophi size), and factors for treatment group, visit, visit by treatment group interaction and visit by baseline-score interaction.

To control the overall Type 1 error rate of the study, taking into consideration the one primary and 5 secondary endpoints, the endpoints will be tested sequentially. For each endpoint, pegloticase with MTX will be tested against pegloticase with placebo for MTX at the 0.0495 level only if pegloticase with MTX was statistically significant for the endpoint preceding it in the prespecified order and 5 secondary endpoints, the endpoints will be tested sequentially. For each endpoint, pegloticase with MTX will be tested against pegloticase with placebo for MTX at either the 0.0495 level only if pegloticase with MTX was statistically significant for the endpoint preceding it in the prespecified order.

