### **9.6.9 Sample Size and Power Considerations**

The response rate during Month 6 on pegloticase 8 mg every 2 weeks was 43% for the phase 3 studies. A sample size of 135 subjects (90 subjects randomized to receive pegloticase with MTX, 45 subjects randomized to receive pegloticase with placebo for MTX) provides 88% power at the 2-sided alpha=0.05 level to detect a difference of 28% (71% response rate for pegloticase with MTX vs. 43% for pegloticase with placebo for MTX).

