#### **2.2.2. Final Analysis**

The primary analysis of all endpoints will be performed after all subjects reach Week 52 in which the primary and secondary efficacy endpoints will be tested at the 0.0495 significance level in

This document is confidential.

sequential order. All other efficacy endpoints are exploratory in nature and will be tested using 2-sided tests at the 5% significance level without multiplicity adjustment.

A follow-up analysis will be performed after all subjects complete the post-treatment follow-up period. The follow-up analysis will only include descriptive summaries of the post-treatment efficacy and safety data.

In addition to the above analyses, blinded safety data will be summarized regularly throughout the study for safety monitoring by the Sponsor.

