### **3.6. Determination of Sample Size**

The response rate during Month 6 on pegloticase 8 mg every 2 weeks was 43% for the phase 3 studies. A sample size of 135 subjects (90 subjects randomized to receive pegloticase with MTX, 45 subjects randomized to receive pegloticase with placebo for MTX) provides 88% power at the 2-sided alpha=0.05 level to detect a difference of 28% (71% response rate for pegloticase with MTX vs. 43% for pegloticase with placebo for MTX).

The COVID-19 pandemic outbreak occurred midway through enrollment for the study, which has affected some subject enrollment and data acquisition during the trial. As a result, the Sponsor has planned to enroll approximately 10 additional subjects (for a total of 145 randomized subjects), in order to obtain information equivalent to studying at least 135 subjects not impacted by COVID-19.

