- 2) A regression model will be created using observed data (after imputation specified in step #1 performed) from subjects not affected by site closures. A linear regression model will be fit for each sUA value comprising Month 6 (i.e., Week 20, Week 21, Week 22, Week 23, Week 24) as the dependent variable and will include independent variables of treatment group, tophi presence, sex, age, baseline weight, race (white, non-white), available pre-infusion sUA values from Day 1 up through the timepoint of each dependent variable, serious AE (yes or no), severe AE (yes or no), and number of gout flares during the Pegloticase + IMM Period up through Month 6.
- 3) Based on the fitted regression model, a new regression model is simulated from the posterior predictive distribution of the parameters, and the predictive mean matching method is used to impute missing values (Rubin 1987, pp. 166–167, Heitjan and Little 1991; Schenker and Taylor 1996). The predictive mean matching method imputes a value chosen randomly from a set of observed subjects with complete data (K=10) whose predicted values are closest to the predicted value for the missing entry from the simulated regression model. This will be implemented using the MI procedure in SAS with the fully conditional specification (FCS) method. Covariates will be removed from the model if the model is unable to converge due to quasi or complete separation. Missing results for covariates will be imputed using either linear regression (for continuous variables) or logistic regression or discriminant function method (for categorical variables).
- 4) The imputation model will be used to create 100 datasets with random number generation. These 100 datasets will include the data from subjects not impacted by COVID-19 and imputed data from subjects with "Site Closure" missing data, resulting in 100 apparently complete datasets.

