### 9.2.3. Analysis of the Primary Endpoint

The analysis of proportion of responders during Month 6 will use Cochran-Mantel-Haenszel (CMH) weighting to estimate the common risk difference within strata and to estimate the standard error of the common risk difference. Stratification for the analysis will use the actual stratification factor value if the subject is misclassified during the randomization. The difference in response rates, comparing pegloticase with MTX vs. pegloticase with placebo, will be estimated along with the corresponding 95% CI and p-value.

If multiple imputation is performed, this analysis will be applied to each of the 100 datasets created after the multiple imputation process specified in [Section 9.2.2](#) has been performed. Results of the 100 analyses on apparently complete data will be pooled using Rubin's rule, resulting in a single estimate for the proportion of responders in each treatment group with two-sided 95% confidence interval, as well as the p-value comparing the randomized treatment groups and a two-sided 95% confidence interval on the difference in response rates. This will be implemented using the MIANALYZE procedure in SAS.

If multiple imputation is not performed (i.e. there are no subjects with missing data due to site closure), the proportion of responders along with a 95% confidence interval for the proportion will be summarized based on the observed data (i.e. with no imputation based on COVID-19 impact), with non-responder imputation used for subjects who meet the stopping rule or have missing results during Month 6. The proportion of sUA < 6 mg/dL responders will be plotted.

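### The primary responder comparison adjusts only for tophi and leaves pre-randomisation sUA and weight unused: a missed efficiency of unknown size, not an error

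*Protocol*

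**What the plan says.** **Primary analysis.** Protocol 9.6.5.1 sets a single adjustment factor: "Stratification for the analysis will use the same factor as was used to stratify randomization, presence of tophi (yes, no". SAP 9.2.3 agrees. The analysis "will use Cochran-Mantel-Haenszel (CMH) weighting to estimate the common risk difference within strata", using the true stratum where a subject was misclassified at randomisation. The supplemental, sensitivity and subgroup analyses (SAP 9.2.4 to 9.2.6) add no baseline covariate to the treatment comparison. The logistic model in SAP 9.2.4 only imputes response for site-closure subjects, and the result goes back through the same CMH method.

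**What is measured before randomisation.** Randomisation is at Week -4 (Protocol 9.1). sUA is scheduled at Screening, Week -6 and Week -4 (Protocol 9.5.1.1), and weight at Screening and Week -6 (Protocol 9.5.4.4). For both, SAP 6.2.1 defines baseline as the last value before the first open-label MTX dose, which is normally Week -6.

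**Practice elsewhere in the plan.** The repeated-measures models for the HAQ endpoints (SAP 9.3.3) and for exploratory continuous endpoints, including change in sUA (SAP 9.4 and 9.4.9), contain the baseline value as well as tophi.

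**Imputation model.** SAP 9.2.2 lists treatment group together with "tophi presence, sex, age, baseline weight, race (white, non-white), available pre-infusion sUA values from Day 1" and onward to the time point being imputed, plus adverse-event indicators and a flare count.

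**The concern.** The primary endpoint is a dichotomised sUA measure. The plan adjusts change in sUA for baseline sUA, but it does not adjust the responder comparison for that value, although it is already in the database. If baseline sUA or weight predicts response, adjusting for it narrows the confidence interval for the same quantity, the difference in response proportions between the randomised arms. No new data are needed.

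Precision matters here because the placebo arm is small: 45 subjects as planned, or about 48 if the enlarged total of 145 is split 2:1. The primary endpoint is also the first step in a fixed testing sequence, so every secondary test depends on it.

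**Working it through.** **Inputs**
- Response rates: "71% response rate for pegloticase with MTX vs. 43% for pegloticase with placebo for MTX" (Protocol 9.6.9).
- Sample size: "90 subjects randomized to receive pegloticase with MTX, 45 subjects randomized to receive pegloticase with placebo for MTX" (Protocol 9.6.9).
- Stated result: the design "provides 88% power at the 2-sided alpha=0.05 level to detect a difference of 28" percentage points (Protocol 9.6.9).
- Operative alpha: "primary and secondary efficacy endpoints will be tested at the 0.0495 significance level" (SAP 2.2.2).
- Share of outcome variance explained by the added covariates beyond tophi (R2): not in the documents, so taken as a range.

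**Step 1. Reproduce the stated power.** The pooled normal approximation with 90 and 45 subjects gives 88.6% at two-sided alpha 0.05 and 88.5% at 0.0495. The plan's 88% therefore reproduces with no covariate adjustment.

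**Step 2. Unadjusted standard error (unpooled).**

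SE = sqrt(0.71 x 0.29 / 90 + 0.43 x 0.57 / 45) = sqrt(0.002288 + 0.005447) = 0.0879

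Power = Phi(0.28 / SE - z), where z is the normal quantile at 1 - 0.0495/2, about 1.964. With 0.28 / 0.0879 = 3.184, power = Phi(1.220) = 88.9%.

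**Step 3. Effect of adjustment.** To a first approximation, covariates that explain a share R2 of the outcome variance multiply the SE by sqrt(1 - R2). The last column, 135 / (1 - R2), is the unadjusted sample size with the same precision.

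| Assumed R2 | SE factor | Power at alpha 0.0495 | 95% CI half-width (points) | Equivalent unadjusted N |
|---|---|---|---|---|
| 0 | 1.000 | 88.9% | 17.2 | 135 |
| 0.02 | 0.990 | 89.5% | 17.1 | 138 |
| 0.05 | 0.975 | 90.4% | 16.8 | 142 |
| 0.10 | 0.949 | 91.8% | 16.4 | 150 |

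The pooled formula gives almost the same values: 88.5%, 89.1%, 90.0% and 91.5%.

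**Step 4. Which covariates qualify.** Week -6 sUA and Week -6 weight precede randomisation, so treatment cannot have affected them. Day 1 sUA precedes the first pegloticase infusion but follows four weeks of randomised MTX or placebo. Later sUA values, adverse events and flares also follow randomisation. These variables are legitimate in an imputation model but not as adjustment covariates in the treatment comparison.

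**The case against.** The strongest reply is that nothing is broken. The analysis follows the stratified randomisation, the type I error rate is unaffected, and the stated power holds without adjustment. All of that stands.

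The gain is also unproven. The protocol's background (7.1.2 and 7.2) links loss of response to anti-drug antibodies, not to baseline sUA or weight. Eligibility narrows the spread of both (sUA at least 7 mg/dL, weight at most 160 kg). The true R2 may therefore be near the bottom of the range. This stands too, and it is why the range starts at zero.

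A reader might infer that the SAP contradicts itself, by relying on baseline sUA to impute the outcome and then dropping it from the comparison. The documents do not support that. The imputation model includes baseline weight, but its sUA predictors begin at Day 1, and the SAP-defined baseline sUA is not listed. Listing a variable there also makes no claim that it strongly predicts response. Imputation is confined to site-closure subjects and may not be needed at all.

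The SAP also raises enrolment ("for a total of 145 randomized subjects"). Without adjustment, a split of about 97 to 48 gives 90.5% power at alpha 0.0495. However, SAP 3.6 intends those extra subjects to offset COVID-19 losses, so they are not clearly spare power.

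Finally, logistic standardisation with a robust SE rests on large-sample theory, and the placebo arm is small. That limits the number of covariates but does not rule out two prespecified ones.

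**Conclusion.** The point holds as a low-priority improvement. The primary analysis is valid and adequately described, but it forgoes adjustment for two values scheduled on every subject before randomisation, while the plan's own continuous-endpoint models adjust for baseline.

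The size of the gain cannot be established from the documents. It is about 0.6, 1.5 or 2.9 percentage points of power if the covariates explain 2%, 5% or 10% of outcome variance beyond tophi (89.5, 90.4 or 91.8 less 88.9), and essentially none at 0%. These figures assume the planned 90 and 45 subjects, response rates of 71% and 43%, and the simple sqrt(1 - R2) scaling. They should not be read as evidence that the trial is underpowered or that its type I error is at risk.

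**What to change.** Before unblinding, amend SAP 9.2.3 so that the primary estimate is the marginal risk difference from logistic-regression standardisation:
- Include treatment, tophi presence, Week -6 sUA and Week -6 weight, and nothing else. Name Week -6 (the SAP 6.2.1 baseline) explicitly so that Day 1 sUA is not used by mistake.
- Use a robust standard error suited to a small placebo arm, and state it in advance.
- Pool over the 100 imputed datasets as now, if imputation is performed.
- Keep the tophi-only CMH risk difference as the supportive analysis.

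The cost is SAP wording, modest programming and a declared departure from the protocol. The protocol fixes the CMH method, and SAP Section 12 currently records no changes. The statistical downside is reliance on large-sample theory with about 45 to 48 placebo subjects, so the covariate list must stay short and fixed. If the sponsor prefers to leave CMH as primary, the adjusted estimate could be prespecified as supplemental. That would add information but would not raise the power of the formal test.
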